Theoretically there are some unproven speculative explanations. The primary tumor may act as a source for ongoing systemic spreading of chemoresistant cancer cells (circulating tumor cells, stem cells) ¹²⁻¹⁵ or metastases proliferation factors (TGFbeta ¹⁶⁻¹⁸, VEGF ¹⁹⁻²⁴) supporting systemic tumor growth and further metastases proliferation. Resection of the primary tumor may thus down regulate the constant release of circulating tumor cells/stem cells and/or proliferating factors ^{25,26} reducing the capacity to produce new metastases and decreasing proliferation of metastases.

The reduction of chemoresistant systemic stem cells by resection of the primary tumor may render metastatic cells chemosensitive. Clinically there is evidence that resection of the primary tumor may enhance the response to systemic therapy^{11,27,28}

Hypothesis

We first hypothesize that the removal of the primary tumor in stage IV breast cancer patients followed by systemic therapy improves median survival compared with no local therapy. In case that this main thesis proves true we secondly hypothesize that the ultimate reason for the improved survival by local therapy may be due to the reduction of stem cells or circulating proliferation factors such as VEGF or TGF beta in the peripheral system as these cells and factors may origin from the primary cancer. This may reduce metastatic growth kinetics and increase chemosensitivity of visceral and non-visceral metastases and prolong median and progression free survival.

Aim

The aim of the study is to investigate the effect of local therapy to the primary tumor in synchronous metastasized breast cancer patients and to evolve the role of circulating tumor cells and growth factors in the peripheral blood.

Study objectives

The primary study objective is

1. to demonstrate that the resection of the primary breast cancer in synchronous metastasized breast cancer patients increases the median survival.

The secondary study objectives are

1. to investigate the role of the primary breast cancer resection in terms of local and distant time to progression
2. to evaluate the role of peripheral circulating tumor cells and growth factors in synchronous metastasized breast cancer patients and whether there is any association between their detection and the median survival in pre-selected centers

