3. to examine whether the resection of the primary breast cancer influences peripheral circulating tumor cells and growth factors in pre-selected centers
4. to investigate the quality of life in both groups

Patients

Sample Size Considerations

A sample of 254 patients will be enrolled in this trial (127 in each group) including a drop out rate of 5%. This assumes that there will be a 48-month accrual period. The median survival of patients with local therapy to the primary tumor should be increased by 50% in comparison to patients without local therapy to have 80% power to detect a hazard ratio of 0.666 with a two-sided significance level of 0.05. The recruitment period is assumed with 4 years. The maximum study duration should be 9 years.

Study design (Appendix 1)

This is a prospective multicenter national randomized study. Patients with a histological verified breast cancer are first screened for any metastatic disease. In cases of visceral or non visceral metastatic spreading (International Union against Cancer UICC M1 = stage IV; Appendix 2) the patient is eligible for the study taking into consideration all inclusion and exclusion criteria listed below. After signed informed consent the patient is randomized to either arm A (local treatment) or Arm B (no local treatment, only on demand). In arm A therapy consists of either breast conserving surgery or mastectomy. For axillary surgery, either axillary dissection level I and II or sentinel node biopsy has to be performed (mandatory) which has only to be followed by axillary dissection in case of macrometastasis of at least one sentinel lymph node, followed by radiotherapy (on centers preference). Surgery of the metastases is not allowed in both treatment arms and may only be performed on demand. This will be considered as protocol deviation. Systemic therapy follows surgery on the centers preference. In arm B only systemic therapy is given on the centers preference. Follow up should be done every 3 months during the first 2 years and from then on every 6 months and should include clinical, radiological and laboratory exams. The median survival is the primary endpoint, while the time to local or distant progression are defined as secondary endpoints.

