Additional we measure circulating tumor cells and growth factors in the peripheral blood at pre-selected centers. Therefore 15ml of blood are drawn before surgery and 1-3 days after surgery (arm A only), as well as before first application of systemic therapy, 3-6 months and 12 months after first application of systemic therapy in both arms.

Quality of life questionnaires are handed out to all patients before surgery or first application of systemic therapy as well as every 6 months after enrollment until 42 months visit.

Inclusion and Exclusion Criteria

Females whose conditions satisfy all of the following criteria are the only patients eligible for this study.

General inclusion criteria

1. Written informed consent must be obtained and documented prior to beginning any protocol specific procedures and according to local regulatory requirements.
2. Patients age ≥ 18 years
3. Eastern Cooperative Oncology Group Performance Status is 0 -2 (Appendix 3)
4. Able to comply with the protocol requirements during the treatment and follow-up period.

Disease specific inclusion criteria

5. Untreated synchronous metastasized invasive carcinoma of the breast with the primary tumor in situ (bilateral synchronous metastasized breast cancer patients are eligible).

6. The primary tumor must be identified and may be any size, however, primary resection with resection free margins must be possible.
7. Invasive adenocarcinoma of the breast on histological examination.
8. The metastatic site must be identified by radiological assessment (Computer Tomography of the chest and the abdomen OR ultrasound and chest x ray for visceral metastases; bone scan AND/OR computer tomography AND/OR magnetic resonance for bone metastases). A biopsy is not necessary.

Exclusion criteria

1. Patients in whom a R0 resection (microscopic free margins) is clinically questionable
2. Inflammatory cancer
3. Patients with brain metastases
4. Patients who are not eligible for general anesthesia and operations
5. Patients without metastatic breast cancer (patients with a tumor marker value (CEA, CA15-3) above normal levels without the radiological proven evidence of metastases are not eligible for the study)
6. Patients with a second untreated malignancy
7. Any previous malignancy treated with curative intent and the patient has not been disease-free for 5 years – exceptions are:
 - a. carcinoma in situ of the cervix
 - b. squamous carcinoma of the skin
 - c. basal cell carcinoma of the skin

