For the secondary endpoint growth factors, circulating tumor cells, stem cells, post intervention measurements are compared with baseline values and tested with the *repeated measures ANOVA*. Correlations between initial or late drop of growth factors, circulating tumor cells, stem cells and median survival or TTP, respectively, will be calculated with the *Spearman rank order correlation test*. The stem cell and growth factors in the tumor will be correlated with the stem cell and growth factor release into the peripheral circulation and known prognostic factors such as her2neu expression and grading as well as survival time. The association with her2neu expression and grading and categorical variables will be assessed by an *ANOVA*. The association with the survival time will be analysed with a *Cox regression*.

Surgical Therapy

Local therapy consists of lumpectomy or mastectomy with a resection free margin of at least 1 mm or more demonstrated on paraffin embedded histological sections. Intraoperative frozen sections are allowed but not definitive for margin assessment. For axillary surgery, either axillary dissection level I and II or sentinel node biopsy has to be performed (mandatory) which has only to be followed by axillary dissection in case of macrometastasis of at least one sentinel lymph node.

Surgery on demand

In the arm B (no local therapy) it may be necessary to perform local therapy on demand (surgery, radiotherapy). Reasons may be uncontrolled bleeding or infected exulcerations with a septic component and no treatment benefit from conservative therapy. This will be considered as protocol deviation. However, the patient's follow up is recorded and data are available for retrospective analyses as intention to treat.

Radiation therapy

Local radiation therapy of the breast may be given according to center policy in therapy arm A. In arm B this will be considered as protocol deviation. Radiation therapy of the metastases is allowed according to center policy in both arms.

Systemic therapy

Chemotherapy or anti-hormone therapy is used according to center policy. The following recommendations should be followed:

1. In cases of radiotherapy and chemotherapy (arm A), radiotherapy should not be given later than 6 months after surgery. Radiotherapy is allowed in parallel to anti-hormonal treatment.

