Bleedings as well as seroma productions are rare and may be observed in 1 to 2% of patients. Most bleedings and hematoma formations may be treated conservatively while only a minority may need to undergo a second operation.

There is, however, a small risk to need a second operation due to positive resection margins. This risk is reduced by the use of intraoperativen frozen section analyses to 6% ([name] et al; data submitted).

Benefit for the patients

The benefit for the patient may be a 10% absolute increase in median survival from 24 to 36 months. More over if the hypothesis is true that the resection of the primary tumor in metastasized patients increases overall survival, the knowledge about carcinogenesis increases substantially. If we are able to demonstrate that circulating tumor cells and/or growth factors released from the primary tumor may be at least in part responsible for this improvement, the doors are open to investigate new therapeutic strategies in these patients such as anti-growth factor antibodies or systemic therapies destroying tumor stem cells. No trial has been published so far answering these important questions which may, in fact, guide us to new aspects of cancer therapy.

ADMINISTRATIVE REQUIREMENTS

Good Clinical Practice

- The study will be conducted in accordance with the International Conference on Harmonisation (ICH) for Good Clinical Practice (GCP) and the appropriate regulatory requirement(s). Essential clinical documents will be maintained to demonstrate the validity of the study and the integrity of the data collected.

Ethical Considerations

- The study will be conducted in accordance with ethical principles founded in the Declaration of Helsinki (see Appendix 5). The IEC will review all appropriate study documentation in order to safeguard the rights, safety and well-being of the patients.

Patient Information and Informed Consent

The principal investigators at each center will ensure that the patient is given full and adequate oral and written information about the nature, purpose, possible risk and benefit of the study. Patients must also be notified that they are free to discontinue from the study at any time. The patient should be given the opportunity to ask questions and allowed time to consider the information provided.

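### The planned correlation of marker drop with survival can address association, but not the hypothesis that resection prolongs survival through that drop

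*Protocol*

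**What the plan says.** - **Protocol, Hypothesis.** The second hypothesis is causal: "the ultimate reason for the improved survival by local therapy may be due to the reduction of stem cells or circulating proliferation factors". It is conditional on a survival benefit: "In case that this main thesis proves true we secondly hypothesize".
- **Protocol, Study objectives.** Secondary objective 2 asks "whether there is any association between their detection and the median survival in pre-selected centers". Secondary objective 3 is "to examine whether the resection of the primary breast cancer influences peripheral circulating tumor cells and growth factors in pre-selected centers".
- **Protocol, secondary endpoints, subsection on growth factors, circulating tumor cells and stem cells.** The fall is related to outcome by a Spearman rank correlation: "Correlations between initial or late drop of growth factors, circulating tumor cells, stem cells and median survival or TTP, respectively, will be calculated with the" test of that name. Post-intervention values are also set against baseline by repeated measures ANOVA. Neither sentence names treatment arm. A Cox regression on survival time closes the paragraph, but it follows the sentences on markers in tumor tissue and names neither the fall in blood nor arm.
- **Protocol, Study design (Appendix 1).** Only arm A has blood taken before surgery and 1-3 days after it; further samples are drawn "as well as before first application of systemic therapy, 3-6 months and 12 months after first application of systemic therapy in both arms". Systemic therapy is left to center policy in both arms.
- **Protocol, Benefit for the patients.** New treatment strategies would open if the trial could show that cells or factors "released from the primary tumor may be at least in part responsible for this improvement".
- **SAP.** Section 3.6.3 leaves the marker analysis to a later version and gives no method. The covariate list in 3.9 contains no marker. Section 5, on changes from the protocol, does not withdraw the correlation.

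**The concern.** The second hypothesis is one of mediation: resection lowers the marker, the lower marker prolongs life, and at least part of the surgical benefit runs along that path. The Spearman null is only that the fall and survival time are unrelated. Rejecting it does not establish the path, because a pooled correlation can arise in two other ways.

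1. *Response to systemic therapy.* The 3-6 and 12 month samples are taken under systemic therapy. Patients who respond can have a larger fall and longer survival, whatever resection does to the marker.
2. *Separate effects of surgery.* If resection lowers an inert marker and prolongs survival by another route, pooling the arms creates a correlation.

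At stake is the trial's mechanistic conclusion. No analysis in the plan is written to test it, and the one that comes closest can be positive when the mechanism is false.

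**Working it through.** **The plan's own figure.** The documents give no sample size, power or effect size for the marker analyses. The stated figure nearby is 192 deaths for the primary test, and it reproduces. Schoenfeld: 4(1.960 + 0.842)²/(ln 0.666)² = 31.40/0.1652 = 190.02, rounded up to 191. Freedman: 7.849 × (1.666/0.334)² = 195.3, rounded up to 196. Power with 192 events is 80.4%. The survival inputs below are therefore the plan's own.

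**Inputs from the protocol (Sample size considerations).** Control median 24 months; hazard ratio 0.666; 1:1 allocation; 4 years of accrual within 9 years, so follow-up runs from 108 − 48 = 60 to 108 months.

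**Assumptions, not in the documents.** The number of patients in pre-selected centers, and how strongly systemic response drives the fall and survival.

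**Route 1, first model (12-month fall).** Resection changes no marker, and the surgical hazard ratio of 0.666 acts elsewhere. Late drop = r × response + noise. Hazard = (ln 2/24) × 0.666^arm × b^response. Patients alive at 12 months are analysed with survival counted from then; 1000 trials per setting. Rejection at nominal 5%, with r = 0.5 and b = 0.7 per SD:

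| Patients | Censored times | Fully observed times |
|---|---|---|
| 60 | 11.5% | 12.2% |
| 100 | 18.6% | 20.1% |
| 150 | 27.3% | 31.1% |

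Repeat runs with censoring gave 13-14%, 18-20% and 24-26%. The second column shows that censoring is not the cause. At 100 patients, over r from 0.3 to 0.7 and b from 0.8 to 0.6, the range is 6.8% to 50.7%. With no link between fall and survival the test rejects in 5-6%, as it should.

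**Route 1, second model.** Drop = 0.5 + 0.7 × response + 0.7 × noise, so the correlation with response is 0.7/√0.98 = 0.71. Response lowers the hazard by a factor of 1.25 or 1.50 per SD (hazard ratio 1/1.25 = 0.80 or 1/1.50 = 0.67). Survival is counted from entry, the surgical hazard ratio is 0.67, and there are 1500 trials per setting:

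| Patients | No link | Factor 1.25 | Factor 1.50 |
|---|---|---|---|
| 40 | 4.4% | 12.5% | 26.5% |
| 60 | 4.8% | 13.8% | 36.9% |
| 100 | 5.2% | 22.7% | 56.8% |
| 254 | 3.7% | 53.1% | 92.9% |

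In the same trials:
- A between-arm comparison of the fall rejects in 4-6.5%, which is correct because resection does nothing to the marker here.
- A post-versus-baseline test without arm rejects in 87-100%, because both arms were given a mean fall of 0.5. It cannot show what resection does.
- Spearman within one arm still rejects in 15-20% at 40-60 patients and 66-69% at 254 (factor 1.50). Splitting by arm alone does not remove confounding by response.

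**Route 2.** With no response link, resection lowers an inert marker by 0.7 or 1.5 units (within-arm SD √0.98 = 0.99) and prolongs survival by another path. Pooled Spearman rejects in 6.7% or 9.7% at 40 patients, rising to 15.3% or 39.1% at 254. Within-arm tests stay at about 4-6%. A separate check gave 8-22% for pooled Spearman against about 3-7% for a Cox model started at the sample date with arm included. An arm term therefore deals with this route.

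**The initial drop.** The protocol does not define it. If it means pre-operative to day 1-3, it exists only in arm A. Study design places systemic therapy after surgery, so response cannot explain that fall. It also has no comparator in arm B. If it means the fall to 3-6 months, route 1 applies to it as well.

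**The case against.** The strongest defence is that the correlation answers a question the protocol does ask. Secondary objective 2 is about association, and for it a response-driven correlation is a true finding. The rates above are then power. They become error rates only if the result is taken as evidence for the mechanism. This stands, and it limits the point to the second hypothesis.

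Four stronger readings are tempting, and the documents do not support them.

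- *That the protocol plans to treat the correlation as proof.* The passage under Benefit for the patients is conditional and names no test. No section assigns the Spearman result to the second hypothesis. The gap is that nothing else is assigned to it either.
- *That arm is excluded.* The text is silent. It can only be said that no arm term is specified, and the same holds for the repeated measures ANOVA, which is the planned look at objective 3.
- *That systemic response confounds every drop.* It does not confound a fall from before surgery to day 1-3.
- *That a mechanism could be claimed with no survival benefit.* The second hypothesis is taken up only if surgery improves survival. This condition does not protect the inference when surgery works: at 100 patients and factor 1.25 the test rejects in 22.7% with a surgical hazard ratio of 0.67, and in 23.4% with 1.00.

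It can also be said that this is an unpowered secondary question and that the SAP defers it. Both are true. The deferral leaves room for the correction but does not supply one.

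**Conclusion.** The point holds for the mechanism and for the late drop. The correlation can serve secondary objective 2. It cannot support the hypothesis that resection prolongs survival by lowering circulating cells or factors, and no other written analysis addresses that hypothesis.

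Under assumed cohorts of 60-150 patients and a moderate response effect, the nominal 5% test rejects in roughly 12-27% of trials when the mechanism is false. A weak effect gives about 7% at 100 patients, and stronger effects or larger cohorts give far more. Cohort size and response strength are assumptions, so these figures show that the problem can be material, not how large it will be in this trial. The primary analysis is unaffected. The correction is worth making before the later SAP version fixes the marker analysis.

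**What to change.** Make three changes in the protocol's marker-analysis subsection and in the SAP version announced in 3.6.3.

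1. For the 3-6 and 12 month falls, replace Spearman with a Cox model started at the sample date, in patients alive then. Include randomised arm, baseline marker level and the prognostic factors already collected. Report it as prognostic association only, not as evidence for the second hypothesis. The arm term handles route 2 but not route 1, so the label is essential.
2. For objective 3, compare baseline-adjusted marker levels between the arms at the scheduled samples common to both, instead of relying on post-versus-baseline change alone. The 3-6 and 12 month samples carry this comparison, because the pre-systemic sample is itself the baseline in arm B.
3. State that an association between fall and survival will not by itself be taken as support for the mechanism. State also that any mediation analysis is exploratory, because the fall is not randomised and confounding by metastatic burden remains.

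A rule that claims mediation from the fall between baseline and the pre-systemic sample is tempting, because that fall precedes systemic therapy. It should not be used. The fall is zero by construction in arm B, so the arm comparison reduces to an uncontrolled change in arm A. Its time origin lies after surgery in one arm and before any treatment in the other. With an inert marker and metastatic burden raising the hazard 1.43-fold per SD (assumed), such a rule claimed mediation in 10.5%, 19% and 24% of simulated trials at 60, 100 and 150 patients; a repeat gave about 7%, 17% and 24%.

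The cost is a wording change and one model plus one between-arm comparison per marker, from samples already scheduled. The price is that the mechanistic claim becomes harder to make.

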Appendix 1: Flow chart randomization and groups

Flow chart randomisation and groups

Appendix 2: Union against cancer (UICC 1987) breast cancer stages

Stage 0	Tis	N0	M0
Stage I	T1	N0	M0
Stage II			
Stage IIa	T0	N1	M0
	T1	N1	M0
	T2	N0	M0
Stage IIb	T2	N1	M0
	T3	N0	M0
Stage III			
IIIa	T3	N1	M0
	T1,T2,T3	N2	M0
IIIb	T4	Any N	M0
	Any T	N3	M0
Stage IV	Any T	Any N	M1

Appendix 3: Eastern Cooperative Oncology Group (ECOG) Performance Status

Grade	ECOG
0	Fully active, able to carry on all pre-disease performance without restriction
1	Restricted in physically strenuous activity but ambulatory and able to carry out work of light or sedentary nature, e.g., light house work, office work
2	Ambulatory and capable of all self-care but unable to carry out any work activities. Up and about more than 50% of waking hours
3	Capable of only limited self-care, confined to bed or chair more than 50% of waking hours
4	Completely disabled. Cannot carry on any self-care. Totally confined to bed or chair
5	Dead

Oken et al Am J Clin Oncol 5:649-655, 1982

Appendix 4: Follow up Flowchart

recommended Assessments & Investigations	YEAR 1				YEAR 2				YEAR 3		YEAR 4		YEAR 5		RELAPSE/PROGRESSION	
	3	6	9	12	15	18	21	24	30	36	42	48	54	60		
Months (± 1 month)	3	6	9	12	15	18	21	24	30	36	42	48	54	60		
History and Clinical Examination																
Intercurrent Medical History	•	•	•	•	•	•	•	•	•	•	•	•	•	•	•	
General and Physical Examination	•	•	•	•	•	•	•	•	•	•	•	•	•	•	•	
Quality of Life		•		•		•		•		•		•		•		
Laboratory (incl CEA, CA 15-3)	According to systemic therapy but at least every 2-4 months										every 5-7 months					
Imaging																
Breast Imaging (check guidance)	(○)	(○)	(○)	•	(○)	(○)	(○)	•	(○)	•	(○)	•	(○)	•	•	
CT ¹ Thorax/Abdomen (US/chest X-ray)	•	•	•	•	•	•	•	•	•	•	•	•	•	•	•	
Bone Imaging	In cases of pre-randomized diagnosed bone metastases every 2-4 months, in case of suspected bone metastases for staging								In cases of pre-randomized diagnosed bone metastases every 5-7 months, in case of suspected bone metastases for staging							
Pregnancy Test ²	in pre/perimenopausal women according to local policy															

¹ Alternatively a PET-CT scan can be performed

² Pregnancy tests have to be performed in pre/perimenopausal women during screening phase and at regular intervals throughout the trial according to local policy

Appendix 5: EORTC QLQ-C30 (version 3.0), QLQ BR 23

GERMAN

EORTC QLQ-C30 (version 3.0)

Wir sind an einigen Angaben interessiert, die Sie und Ihre Gesundheit betreffen. Bitte beantworten Sie die folgenden Fragen selbst, indem Sie die Zahl ankreuzen, die am besten auf Sie zutrifft. Es gibt keine "richtigen" oder "falschen" Antworten. Ihre Angaben werden streng vertraulich behandelt.

Bitte tragen Sie Ihre Initialen ein:

--	--	--	--

Ihr Geburtstag (Tag, Monat, Jahr):

--	--	--	--	--	--

Das heutige Datum (Tag, Monat, Jahr):

31					
----	--	--	--	--	--

	Überhaupt			
	nicht	Wenig	Mäßig	Sehr
1. Bereitet es Ihnen Schwierigkeiten sich körperlich anzustrengen (z.B. eine schwere Einkaufstasche oder einen Koffer zu tragen?)	1	2	3	4
2. Bereitet es Ihnen Schwierigkeiten, einen längeren Spaziergang zu machen?	1	2	3	4
3. Bereitet es Ihnen Schwierigkeiten, eine kurze Strecke außer Haus zu gehen?	1	2	3	4
4. Müssen Sie tagsüber im Bett liegen oder in einem Sessel sitzen?	1	2	3	4
5. Brauchen Sie Hilfe beim Essen, Anziehen, Waschen oder Benutzen der Toilette?	1	2	3	4

Während der letzten Woche:

	Überhaupt			
	nicht	Wenig	Mäßig	Sehr
6. Waren Sie bei Ihrer Arbeit oder bei anderen tagtäglichen Beschäftigungen eingeschränkt?	1	2	3	4
7. Waren Sie bei Ihren Hobbys oder anderen Freizeitbeschäftigungen eingeschränkt?	1	2	3	4
8. Waren Sie kurzatmig?	1	2	3	4
9. Hatten Sie Schmerzen?	1	2	3	4
10. Mussten Sie sich ausruhen?	1	2	3	4
11. Hatten Sie Schlafstörungen?	1	2	3	4
12. Fühlten Sie sich schwach?	1	2	3	4
13. Hatten Sie Appetitmangel?	1	2	3	4
14. War Ihnen übel?	1	2	3	4
15. Haben Sie erbrochen?	1	2	3	4

Bitte wenden

Während der letzten Woche:

	Überhaupt nicht	Wenig	Mäßig	Sehr
16. Hatten Sie Verstopfung?	1	2	3	4
17. Hatten Sie Durchfall?	1	2	3	4
18. Waren Sie müde?	1	2	3	4
19. Fühlten Sie sich durch Schmerzen in Ihrem alltäglichen Leben beeinträchtigt?	1	2	3	4
20. Hatten Sie Schwierigkeiten sich auf etwas zu konzentrieren, z.B. auf das Zeitunglesen oder das Fernsehen?	1	2	3	4
21. Fühlten Sie sich angespannt?	1	2	3	4
22. Haben Sie sich Sorgen gemacht?	1	2	3	4
23. Waren Sie reizbar?	1	2	3	4
24. Fühlten Sie sich niedergeschlagen?	1	2	3	4
25. Hatten Sie Schwierigkeiten, sich an Dinge zu erinnern?	1	2	3	4
26. Hat Ihr körperlicher Zustand oder Ihre medizinische Behandlung Ihr Familienleben beeinträchtigt?	1	2	3	4
27. Hat Ihr körperlicher Zustand oder Ihre medizinische Behandlung Ihr Zusammensein oder Ihre gemeinsamen Unternehmungen mit anderen Menschen beeinträchtigt?	1	2	3	4
28. Hat Ihr körperlicher Zustand oder Ihre medizinische Behandlung für Sie finanzielle Schwierigkeiten mit sich gebracht?	1	2	3	4

Bitte kreuzen Sie bei den folgenden Fragen die Zahl zwischen 1 und 7 an, die am besten auf Sie zutrifft

29. Wie würden Sie insgesamt Ihren Gesundheitszustand während der letzten Woche einschätzen?

1	2	3	4	5	6	7
sehr schlecht						ausgezeichnet

30. Wie würden Sie insgesamt Ihre Lebensqualität während der letzten Woche einschätzen?

1	2	3	4	5	6	7
sehr schlecht						ausgezeichnet

EORTC QLQ - BR23

Patienten berichten manchmal die nachfolgend beschriebenen Symptome oder Probleme. Bitte beschreiben Sie, wie stark Sie diese Symptome oder Probleme während der letzten Woche empfunden haben.

Während der letzten Woche:	Überhaupt			
	nicht	Wenig	Mässig	Sehr
31. Hatten Sie einen trockenen Mund?	1	2	3	4
32. War Ihr Geschmacksempfinden beim Essen oder Trinken verändert?	1	2	3	4
33. Schmerzten Ihre Augen, waren diese gereizt oder trännten sie?	1	2	3	4
34. Haben Sie Haarausfall?	1	2	3	4
35. Nur bei Haarausfall ausfüllen: Hat Sie der Haarausfall belastet?	1	2	3	4
36. Fühlten Sie sich krank oder unwohl?	1	2	3	4
37. Hatten Sie Hitzewallungen?	1	2	3	4
38. Hatten Sie Kopfschmerzen?	1	2	3	4
39. Fühlten Sie sich wegen Ihrer Erkrankung oder Behandlung körperlich weniger anziehend?	1	2	3	4
40. Fühlten Sie sich wegen Ihrer Erkrankung oder Behandlung weniger weiblich?	1	2	3	4
41. Fanden Sie es schwierig, sich nackt anzusehen?	1	2	3	4
42. Waren Sie mit Ihrem Körper unzufrieden?	1	2	3	4
43. Waren Sie wegen Ihres zukünftigen Gesundheitszustandes besorgt?	1	2	3	4

Während der letzten vier Wochen:	Überhaupt			
	nicht	Wenig	Mässig	Sehr
44. Wie sehr waren Sie an Sex interessiert?	1	2	3	4
45. Wie sehr waren Sie sexuell aktiv? (mit oder ohne Geschlechtsverkehr)?	1	2	3	4
46. Nur ausfüllen, wenn Sie sexuell aktiv waren: Wie weit hatten Sie Freude an Sex?	1	2	3	4

[figure not shown]
Bitte wenden

Während der letzten Woche:

	Überhaupt			
	nicht	Wenig	Mässig	Sehr

47. Hatten Sie Schmerzen in Arm oder Schulter?	1	2	3	4
48. War Ihr Arm oder Ihre Hand geschwollen?	1	2	3	4
49. War das Heben oder Seitwärtsbewegen des Arms erschwert?	1	2	3	4
50. Hatten Sie im Bereich der betroffenen Brust Schmerzen?	1	2	3	4
51. War der Bereich Ihrer betroffenen Brust angeschwollen?	1	2	3	4
52. War der Bereich der betroffenen Brust überempfindlich?	1	2	3	4
53. Hatten Sie Hautprobleme im Bereich der betroffenen Brust (z.B. juckende, trockene oder schuppende Haut)?	1	2	3	4

